### 8.3.1.2 Handling of Missing data

Following the random process, the additional visits were presented as missing rows which were handled based on the below rules:

- The same set of baseline covariates (e.g., age, region, baseline FEV1) for the same patients were carried over to the missing rows;
- Missing data on temporal variables were placed by nominal time (see section 9.4).

Missing data on dependent variable, change in  $FEV_1$  at Week 48 from baseline, were imputed based on multiple imputation model assuming missing at random (MAR) mechanism. The set of variables included in the multiple imputation model were region, age group, baseline  $FEV_1$  and temporal (time) variables. The number of imputed datasets generated was 100. The number of datasets generated were 10000 with 100 imputations within each of the 100 complete datasets.

#### 8.3.1.3 Linear Mixed Model

A linear mixed model (LMM) for repeated measurements, similar to the analysis of the primary endpoint (section 14.1) was performed to model FEV1 measurements for each complete dataset. Since the IA was blinded, the treatment group, and the interactions of time splines by treatment were excluded from the model.

The model included change in  $FEV_1$  between baseline and subsequent visits as the dependent variable, and contain the following covariates (except from the intercept):

- Time splines:  $S_1=t$ ,  $S_2=t^2$ ,  $S_3=t^3$  and  $S_4=max(t-182,0)^3$  where t is the study day of the measurement and  $S_4=(t-182)^3$  if t>182 and 0 otherwise;
- base FEV1: Baseline FEV1;
- base\_FEV1\*S1,..., base\_FEV1\*S4: The interactions of time splines with the baseline FEV1;
- region: North America versus all other countries together;
- age group: age ( $< 55 \text{ versus} \ge 55 \text{ years}$ ).

In case the model did not converge, or the covariance matrix was not positive definite, consideration was taken to drop from the model the highest order random effect.

The adjusted mean change from baseline at Week 48 derived from the LMM was adjusted at the mean baseline FEV1 for all patients who were observed to complete the study or discontinued, not the mean of the covariates over all observations.

Final Version 5.0 Page 21 of 76

Results from each complete dataset was combined using Rubin's rule to provide the least square means (LSMs) for change at Week 48 from baseline as well as the standard error of the LSM. Let seall denote the estimated standard error of the mean change from baseline of FEV1 at Week 48.

The median of squared standard error over all complete datasets can be written as:

$$se_{all.median}^2 = v^2/(n_{complete} + w n_{drop-out})$$
,

where  $n_{complete}$  and  $n_{drop-out}$  denote the number of completer patients (i.e., having a 48 weeks measurement) and the number of patients who dropped-out, respectively, and w is the average weight of the drop-outs. The weight of the completer patients is by definition 1, and w (<1) quantifies the average contribution of the drop-outs to the estimation of the mean change from baseline of FEV1 at Week 48. The variance v2 is the residual variance of the change from baseline of FEV1 at Week 48 after adjustment for the covariates.

Then we remove the rows of the drop-outs and calculate the standard error again. The median of squared standard error is now written as

$$se_{complete,median}^2 = v^2/n_{complete}$$
.

From the two equations, one can solve for v and w. The resulting v disregards the treatment group, so it is larger than the pooled within treatment group variance if the treatment effect is unequal to zero. Under the alternative hypothesis used in the original sample size calculation,  $H_l$ :  $\delta = 200 \text{ mL}$  (0.2 L), the pooled within groups residual variance estimate can be estimated as  $v^2 - \delta^2/4$  (see Kieser and Friede [1]). This value can be used in the sample size formula for the independent samples t-test to calculate the effective sample size  $n_{effective}$  needed for a certain power, or for calculating the power for a given  $n_{effective}$ . The corresponding number of randomized patients is  $n_{randomized} = n_{effective}/(1-\pi+\pi w)$ , where  $\pi$  is the probability of dropping out, estimated by a Kaplan-Meier analysis based on the observed data at the time of the IA.

The independent statistician had provided the Sponsor with the recommended sample size, defined as:

```
n_{recommended} = maximum [110, n_{updated}].
```

Here  $n_{updated}$  is the total number of patients that has to be randomized in order to have 80% power against a treatment effect of 200 mL (0.2 L).

A sensitivity analysis was conducted for the sample size re-estimation by considering patients who have completed Week 48 or have discontinued when calculating the standard error of the change from baseline to Week 48 for FEV1 measurements. The data were fitted using the same LMM for primary analysis for sample size re-estimation without any imputation. The LSM as well as its associated standard error overall were reported with all data under sensitivity analyses and data excluding drop-outs, respectively.

Final Version 5.0 Page 22 of 76

### 8.3.1.4 Analysis of Covariance

Since one of the objectives of the IA was to verify appropriateness of the analysis based on the anticipated longitudinal model vs the analysis based on the ANCOVA model, the sample size calculation was performed also assuming that the final model will be ANCOVA, so that if the decision were to conduct ANCOVA, the power information on this analysis was not missing.

The imputation method described for LMM was repeated and each of the complete datasets after imputation was then analyzed in an ANCOVA model adjusting for region, age group, and baseline FEV1 as a continuous covariate. Time variables were not included as only Week 48 was analyzed for ANCOVA.

Results from each complete dataset were combined using Rubin's rule to provide the LSMs for change in FEV1 at Week 48 from baseline as well as standard error of the LSM.

The adjusted mean change from baseline at Week 48 derived from the ANCOVA was adjusted at the mean of the other covariates at baseline for all patients who had completed the study at the time of the IA, not the mean of the covariates over all observations.

The median of squared standard error over all complete datasets is now written as:

$$se_{complete,median}^2 = v^2/n_{complete}$$
.

One could solve for v. The resulting v disregards the treatment group, and is larger than the pooled within treatment group variance if the treatment effect is unequal to zero. Under the alternative hypothesis used in the original sample size calculation,  $H_1$ :  $\delta = 200$  mL (0.2 L), the pooled within groups residual variance estimate could be estimated as  $v^2 - \delta^2/4$  (see Kieser and Friede [1]). This value could be used in the sample size formula for the independent samples t-test to calculate the effective sample size  $n_{effective}$  needed for a certain power, or for calculating the power for a given  $n_{effective}$ . The corresponding number of randomized patients is  $n_{randomized} = n_{effective}/(1-\pi)$ , where  $\pi$  is the probability of dropping out, estimated by a Kaplan-Meier analysis based on the observed data at the time of the IA.

The independent statistician was to provide to the Sponsor with the recommended sample size, defined as:

```
n_{recommended} = maximum [110, n_{updated}].
```

Here  $n_{updated}$  is the total number of patients that has to be randomized in order to have 80% power against a treatment effect of 200 mL (0.2 L).

# 8.3.2 Interim Analysis for missing values evaluation

In accordance with the previous versions of the protocol (version 4.0 and below), the other objectives of the IA were:

Final Version 5.0 Page 23 of 76

- Evaluation of the actual amount of FEV1 data collected at all timepoints using the spirometer;
- Evaluation of the number of drop-outs and the number and pattern of the missing data;
- Evaluation of the appropriateness of the analysis based on the anticipated longitudinal model vs the analysis based on the ANCOVA model in the light of the collected data.

These objectives were evaluated by means of descriptive statistics on the actual amount of FEV1 data, number of discontinued patients and number of missing data at each study visit.

Pattern of the missing data were evaluated by number of missing values either due to drop-outs or data not collected at each timepoints (intercurrent missing values).

### 8.3.3 Communication of IA results to Sponsor and Investigators

Recommendations were communicated as described in the IACP. The IA was performed by the independent, blinded statistician and delivered on 01 December 2021. The recommendations were as reported in Table 1.

Table 1: LA	l recommend	lations.
-------------	-------------	----------

	Section	Recommendation
1	Sample Size Re-estimation using LMM with multiple imputation - Primary Analysis	The recommendation is to continue with the initial sample size (110 patients) as the reestimating sample size is lower than the initial estimate.
2	Sample Size Re-estimation using LMM - Sensitivity Analysis	LMM Sensitivity analysis supports the findings in the primary analysis. The analysis is only for information purpose due to low sample sizes.
3	Sample Size Re-estimation using ANCOVA with multiple imputation	The recommendation is to increase the sample size to a total number of 152 in order to preserve the pre-specified power.

Final Version 5.0 Page 24 of 76

#### Section

# OTHER OBJECTIVES. It may be concerning when using anticipated longitudinal model as there may be a few data collected at intermediate timepoints between Week 4 and Week 48

#### Recommendation

Protocol Number:

The completion rates are preserved at above 67% level and are fluctuated across the visits.

There is no clear missing trend that can be observed from the data.

In light of the collected data, the recommendation is to continue to the analysis based on the LMM as there is no early indication for trending of missing data.

The blinded statistician communicated these conclusions to the Sponsor. Confidentiality of results was ensured, and no IA results were provided to the Sponsor or the Investigators.

# 8.3.4 Final decision on appropriateness of primary analysis: LMM vs. ANCOVA.

The recommendations from the blinded statistician (December 1st, 2021) have been evaluated

- to continue to strive to achieve the originally planned total patient number of 220 for both clinical trials combined (BOSTON-1 and BOSTON-2) and revise the BOSTON-2 protocol and the new sample size accordingly.
- to implement efforts to minimize missing data in both studies. In general, all patients who maintain consent to be followed for additional outcome information, including patients who discontinue study treatment, should remain in the study for all important safety and efficacy assessments for the full duration of the trial.
- to clearly pre-specify a primary analysis (the meeting package indicates that the primary analysis may be based on ANCOVA, if the LMM model is not viable at the end of the study, in light of the ongoing COVID-19 pandemic). Modifications to the analysis of the endpoints should be reflected in an updated statistical analysis plan before locking the database and prior to viewing any comparative analysis results.

Based on the above considerations, the LMM is deemed applicable, and it will be used for the primary analysis, while ANCOVA will be used as sensitivity analysis, in addition to sensitivity analyses assessing robustness on missingness mechanism and LMM.

Final Version 5.0 Page 25 of 76

### 8.5 Data Monitoring Committee and Confidentiality of Results

An independent Data Monitoring Committee (DMC) will be established to monitor the safety of the IMP throughout the conduct of BOSTON-1 and BOSTON-2 studies. The DMC will monitor safety by evaluating the safety analysis generated by the unblinded independent statistician during the course of the clinical trial. Details of the safety analyses will be included in the DMC's Charter (from occion). The DMC will evaluate the treatment groups for possible trends in AEs, determine whether the basic clinical trial assumptions remain valid, evaluate whether the overall integrity, scientific merit and conduct of the clinical trials remain acceptable, and make recommendations to the Sponsor.

The DMC will perform a comparison between the rate of observed COVID-19 cases, rate of patients' withdrawal, and rate of missing data among trial participants in both treatment arms.

Members of the DMC will be unblinded to the treatment group label, i.e., the DMC will know which group is L-CsA + Standard of Care and which group is Standard of Care alone. The DMC will evaluate all safety and acute tolerability parameters as detailed in the DMC charter.

Safety and acute tolerability parameters include AEs, acute tolerability of L-CsA, infections, malignancies, clinical laboratory data (white blood cell count with differential, red blood cell count, platelet count, alkaline phosphatase, alanine aminotransferase, aspartate aminotransferase, gamma glutamyl transferase, blood urea nitrogen, serum bilirubin, serum creatinine), vital signs, physical examinations and FEV1. The statistics provided will be merely descriptive.

Final Version 5.0 Page 26 of 76

Criteria for membership, responsibilities, meeting frequency, and identification of data listings, summaries and analyses to be provided to the DMC are detailed in the DMC charter.

Statistical analyses to be provided to DMC are planned in a specific DMC SAP.

### 8.6 Adjudication Committee

The AC – consisting of three independent physicians, with documented expertise in the clinical management of lung transplantation and diagnosis and treatment of BOS - will maintain the role of reviewing the BOS progression data in blind condition once each participating patient completes the study period, with the aim to ensure consistent and complete recording of data. If necessary, the AC may query the sites to ask for clarifications. In case there are discrepancies between the assessment of the AC and that of the Investigator regarding BOS progression events, the CRO will notify the Investigator. In all cases, the final decision as to whether or not specific event qualifies as BOS progression stands with the Investigator.

#### 9 **DEFINITIONS**

#### 9.1 Protocol Deviations

Major protocol deviations (PDs) are defined as those deviations from the clinical trial protocol for which there could be a significant influence on the assessment of the treatment efficacy. The impact of major protocol deviations on the efficacy results will be investigated by assessing the robustness of the clinical trial results and conclusions to the choice of analysis population, both including and excluding data potentially affected by major protocol deviations. Please note that other study documents may refer to the major PDs as important PDs, and minor PDs as non-important PDs. The SAP and TFL shells will be using the terminology major and minor PDs. For the study, a PD List has been pre-specified. The PD list contains the list of all study PDs, the categorization, the criticality [Major (important) or Minor (non-important)], the potential impact on analysis populations. All the processes around the collection and the review of PDs are described in detail in the study PD Management Plan.

# 9.2 Analysis Data Sets

The term analysis data set is used to define the set of patients to be included in a class of analyses. The analysis data set is described in terms of the specific criteria for patient inclusion.

Eligibility for the analysis data sets will be determined in a blinded Data Review Meeting (DRM) held after closing, but before locking the database and then producing the final analysis. The blinded DRM will be used to determine if patients should be excluded from the Per-Protocol Set (PPS) in cases of significant and major protocol deviations that would interfere with the assessment

Final Version 5.0 Page 27 of 76

of treatment efficacy. The protocol deviations and their impact are routinely collected and assessed during the conduct of the study.

### 9.2.1 Safety Analysis Set (SAF)

The SAF is defined as all randomized patients receiving SoC and/or at least one dose of L-CsA, independently of the treatment allocation at randomization. As per IE criteria, randomized patients should be already in SoC at enrollment, therefore it is expected that all randomized patients will enter the SAF population.

Independently of the treatment allocation at randomization, patients will be analyzed according to the treatment they actually received:

- L-CsA plus SoC group: for all randomized patients receiving at least one dose on IMP (L-CsA);
- SoC group: for all randomized patients not receiving any dose on IMP (L-CsA) but treated with SoC.

All data collected after baseline to the end of clinical trial participation will be included in the safety summaries.

All safety and tolerability data will be summarized and analyzed using the SAF.

### 9.2.2 Full Analysis Set (FAS)

The FAS is defined as all randomized patients. Patients will be analyzed according to the treatment group to which they were randomized. All primary, CCI endowned using the FAS, unless otherwise specified.

# 9.2.3 Interim Analysis Full Analysis Set (IA-FAS)

The IA-FAS is a subset of the FAS population, used for running the blinded IA foreseen by the study protocol; it included patients who had a baseline and had completed Week 24, or discontinued at the cutoff date, 30-Sep-2021.

No significant, major protocol deviations were identified for the IA-FAS.

Patients were analyzed according to the treatment group to which they were randomized.

The IA-FAS was only used for the IA completed on December 2021, and no further analyses or summaries were or will be produced for the IA-FAS.

# 9.2.4 Per Protocol Set (PPS)

The PPS is defined as all patients included in the FAS

Final Version 5.0 Page 28 of 76

- who complete randomized treatment as scheduled or who are withdrawn prematurely due to lack of efficacy or lack of tolerability of the clinical trial treatment, and
- for whom no major protocol deviations interfering with the assessment of treatment efficacy are observed.

For selected efficacy endpoints, including the primary endpoint, the PPS may be used as a supplementary analysis to assess the impact of drop-outs and major protocol deviations on the results.

Lack of efficacy is defined by the withdrawn reason "Lack of efficacy" as collected in the End Of Study CRF form. Lack of tolerability is defined by the withdrawn reason "Adverse Event (Including SAE/Death)" as collected in the End Of Study CRF form.

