#### Premature termination of clinical trial participation:

- Patients may discontinue participation in the clinical trial at any time by revoking their informed consent.
- The Investigator may withdraw a patient at any time if it is in the best interest of the patient based upon clinical assessments.
- Patient is lost to follow-up.
- Re-transplantation. Patients who are eligible for and/or listed for re-transplantation will continue to participate in the trial until they receive re-transplantation surgery.
- Pregnancy (the patient will be followed via a pregnancy registry).
- Zambon SpA may choose to terminate the study at a site or as a whole for reasons such as, but not limited to, medical futility, safety concerns, or poor study site performance.

Patients stopping to take study treatment but not revoking their consent will be encouraged to continue the visits planned until the scheduled end and perform all the important safety and efficacy assessment for the full duration of the study.

If the patient fails to return for clinical follow-up, the patient will be contacted by telephone or a letter will be sent requesting a mandatory clinic visit and the reason for non-compliance will be documented.

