#### 12.1.4 Re-transplantation

Re-transplantation is defined as the date that a patient undergoes lung re-transplantation surgery. The reason for re-transplantation will be recorded. At the time of re-transplantation, the patient will be withdrawn from the study.

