### 14.1.3 Analysis Model

The primary efficacy analysis will be carried out using a LMM for repeated measurements, using all observed available  $FEV_1$  measurements. In case of death or re-transplantation events,  $FEV_1$  will be imputed as zero at each nominal day post event.

The dependent variables are the absolute change from baseline of FEV1 measurements at visit 2 (i.e., the first post-baseline visit) through visit 9 (Week 48). For the definition of baseline FEV1 please refer to section 8.1.1.

A flexible and robust model will be chosen for the random part of the LMM according to a prespecified stepwise procedure (see next section). The fixed part of the LMM is specified as follows: the model will contain (except from the intercept) time cubic splines, treatment, the interactions of time splines by treatment, baseline FEV1, the interactions of time splines with the baseline FEV1, region (North America versus all other countries together), age (< 55 versus  $\ge 55$  years), and use of azithromycin at randomization (i.e. Baseline, Visit 1).

The primary efficacy parameter will be estimated from the model by the adjusted difference between treatment groups in mean FEV1 change from baseline after 48 weeks. The p-value for the null hypothesis of no difference and a two-sided 95% confidence interval for the difference will be provided.

Superiority of L-CsA will be demonstrated by a statistically significant result (defined as p<0.025, one-sided) in favor of the L-CsA plus SoC treatment compared to SoC alone.

The above comparison between treatment groups at all the other visits (2-8) will also be presented.

A figure of observed mean change from baseline and standard errors at each visit, by treatment group will be presented. A figure with adjusted mean changes from baseline at each visit by treatment group derived from the LMM will be provided.

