#### 14.3.1 PPS

The population for the primary estimand will be altered from the FAS to the PPS. The analysis will be conducted as described for the primary endpoint.

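### The Per Protocol Set provides for deaths but has no rule for re-transplantation, so whether these treatment failures stay in depends on the withdrawal reason recorded

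*SAP*

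**What the plan says.** **Who is in the PPS.** SAP 9.2.4 takes patients from the full analysis set (FAS) "who complete randomized treatment as scheduled or who are withdrawn prematurely due to lack of efficacy or lack of tolerability" who also have no major deviation affecting the efficacy assessment. Protocol 15.1 has the same two conditions. The SAP then ties each withdrawal reason to one entry on a form: "Lack of efficacy is defined by the withdrawn reason 'Lack of efficacy' as collected in the End Of Study CRF form", and "Lack of tolerability is defined by the withdrawn reason 'Adverse Event (Including SAE/Death)' as collected in the End Of Study CRF form".

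**What happens at re-transplantation.** Protocol 12.1.4 states: "At the time of re-transplantation, the patient will be withdrawn from the study". Protocol 9.6.1 lists re-transplantation as a separate ground for ending participation: "Patients who are eligible for and/or listed for re-transplantation will continue to participate in the trial until they receive re-transplantation surgery".

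**How the event is scored.** SAP 14.1.3 sets FEV1 to zero at each later nominal day "In case of death or re-transplantation events".

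**How the PPS analysis is run.** SAP 14.3.1 changes only the population and otherwise follows the primary analysis: "The population for the primary estimand will be altered from the FAS to the PPS".

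**The concern.** Death and re-transplantation are the two events that the SAP version 5.0 composite strategy counts as treatment failure. The PPS definition accommodates one of them by name and is silent on the other. It is also a closed rule: a patient who leaves early without one of the two listed reasons is out.

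A re-transplanted patient with no deviation, on treatment up to surgery, can therefore be removed from the PPS because of the outcome. Adherence and conduct play no part. If the two arms differ in the number removed this way, the PPS and FAS estimates will differ for that reason, and a reader could mistake the gap for an effect of adherence or protocol deviations. The arm that loses more re-transplanted patients is flattered.

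The likely origin is a change that was not carried through. Under Protocol 15.2.3.1, values after re-transplantation were to be modelled as if the event had not happened, so leaving such patients out of the PPS removed no imputed failure. SAP version 5.0 turned them into zeros. Its version history lists the sections changed for this purpose, and neither 9.2.4 nor 14.3.1 is among them.

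**Working it through.** **Step 1. Follow two patients through the text.** Both are on randomized treatment, have no major deviation, and have the event before Week 48.

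| Question | Patient dies | Patient is re-transplanted |
|---|---|---|
| Completes treatment as scheduled? | No | No; withdrawn at surgery (Protocol 12.1.4) |
| FAS primary analysis (SAP 14.1.3) | FEV1 = 0 after the event | FEV1 = 0 after the event |
| Event named in a qualifying PPS reason (SAP 9.2.4)? | Yes, in the adverse-event reason | No |
| In the PPS? | Yes, if recorded under that reason | Only if the site records lack of efficacy or an adverse event |
| PPS analysis (SAP 14.3.1) | FEV1 = 0 | FEV1 = 0 if in the set, otherwise absent |

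Protocol 14 asks for an early End of Treatment evaluation before re-transplantation where possible. That does not amount to 48 weeks of treatment, so it does not make the patient a completer.

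**Step 2. Can re-transplantation be read as lack of efficacy?** The SAP keeps them apart. Table 5 gives re-transplantation and study discontinuation for lack of efficacy separate rows with different handling, and SAP 14.3.6 names death, re-transplantation and lack of efficacy as three events. Table 5 sets re-transplantation to zero in every analysis it covers, including both while-on-treatment analyses, where death is not imputed.

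**Step 3. Illustrate the size.** The documents give no figure for this point. The only yardstick is the 200 mL design difference in SAP 8.2. The sample size built on it reproduces: with an SD of 350 mL, one-sided alpha of 0.025 and 80% power, the t-test needs 49.05 per arm, which rounds up to the stated 50 (power 0.81 at 50).

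Inputs:
- m = 84 per arm, from 169 randomized 1:1 (169/2 = 84.5; SAP 8.2 and 7.2).
- B, baseline FEV1: 1.5 to 2.5 L. Assumed; not in the documents.
- d, mean decline in the other patients: 0.1 to 0.3 L. Assumed; not in the documents.
- k, re-transplanted patients excluded from one arm: 1, 2 or 4. Assumed.

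The arm mean change with the zeros kept is [−(m − k)d − kB]/m. With them dropped it is −d. The shift is therefore k(B − d)/m.

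- Lowest: B = 1.5, d = 0.3 gives 1.2/84 = 14.3 mL per patient.
- Highest: B = 2.5, d = 0.1 gives 2.4/84 = 28.6 mL per patient.

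| Excluded from one arm | Shift in that arm's raw mean |
|---|---|
| 1 | 14 to 29 mL |
| 2 | 29 to 57 mL |
| 4 | 57 to 114 mL |

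With the same B, d and m in both arms, only the imbalance moves the treatment difference; equal numbers excluded give no shift. If more SoC patients are excluded, the PPS estimate is less favourable to L-CsA than the FAS estimate. If more L-CsA patients are excluded, it is more favourable.

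**The case against.** **The form has not been seen.** A reader might infer that re-transplanted patients have no way into the PPS. The documents do not show that. Membership turns on the End of Study form, whose list of reasons is not included. Protocol 9.6.1 cannot stand in for it, because it contains neither of the two reasons that SAP 9.2.4 takes from the form. Protocol 12.1.2 makes re-transplantation a criterion of BOS progression, so a site could reasonably choose lack of efficacy. Unscheduled hospitalization is a serious adverse event under Protocol 12.1.9, which opens a second route, although Protocol 13.1.1.4.4 takes endpoint-related worsening out of adverse events. This stands, and it limits the point to a missing rule. What remains is that membership depends on a coding choice. The Investigator completes the form (Protocol 10.3), and Protocol 9.3.1 leaves treating physicians and study coordinators unblinded.

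**A blinded review settles membership.** Protocol 10.3.2 and SAP 9.2 provide for a blinded data review meeting, which SAP 9.2 places before database lock. That is a real safeguard on timing and blinding. The meeting applies the set definitions, however, and on this event the definition gives it no answer.

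**The PPS is meant to remove drop-outs.** SAP 9.2.4 gives the impact of drop-outs as one of its purposes, so some difference from the FAS is intended. That is fair, but it does not explain why one failure event is provided for by name and the other is not.

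**It is minor.** SAP 9.2.4 makes use of the PPS optional, and Protocol 15.2.3.1 expects these events to be rare. The analysis is indeed secondary to the FAS. Still, SAP 14.3.1 and Protocol 15.1 both plan the PPS analysis of the primary endpoint outright.

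**Conclusion.** The point holds as a gap in a stated rule. SAP 9.2.4 keeps deaths through a named reason and gives none for re-transplantation, although both events score zero in the analysis that the PPS is meant to repeat. Following the text literally either drops these failures because of their outcome or leaves their inclusion to site coding.

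Two stronger readings are not supported. The primary result is not biased by this: the FAS contains every randomized patient, and re-transplanted patients stay in it at zero. Nor do the documents establish a bias of any given size in the PPS. The figure of 14 to 29 mL per excluded patient rests on assumed baselines and declines, uses raw means instead of the spline mixed model, and takes 84 per arm although the PPS will be smaller. The number of events and their split between arms are unknown. The illustration shows only that a few unbalanced exclusions could be visible against 200 mL.

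**What to change.** Before database lock, add to SAP 9.2.4: *Patients who die or are re-transplanted before Week 48 while still on randomized treatment, with no major protocol deviation before the event, count as treatment failures and remain in the PPS with FEV1 imputed as in Section 14.1.3, regardless of which End of Study reason records the event.* If the sponsor prefers to leave re-transplanted patients out, the SAP should say so and give the reason.

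The on-treatment condition matters. Without it, the sentence would admit patients who had stopped L-CsA for a non-qualifying reason and had the event months later, which would weaken the completion criterion. Such patients stay under the existing wording and remain a matter for the blinded review. The SAP should also state whether a temporary interruption just before the event counts as being on treatment.

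The cost is one sentence and a small change to the PPS derivation, which must use event dates as well as the form reason. The date and reason for re-transplantation are already provided for in Protocol 12.1.4. The PPS becomes slightly broader. No visit, data item or treatment rule changes.
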